**Table 4. Efficacy Endpoint Summary for Phase II (Adults Only)**

| Phase II Endpoint                | Primary Summary and Analysis Method  | Sensitivity Analysis   |
|----------------------------------|--|--|
| Primary Endpoint                 |  |  |
| CR/CRh*                          | 
 
Summary statistics of CR/CRh* rate within first 2 cycles. The rate will be estimated along with its 95% exact CI. FAS subjects without response assessment will be treated as non-responders.
 
                | 
 
Repeat the analysis for subjects in the FAS who had non-missing post-baseline response data.
 
May repeat the analysis for PPS when deemed appropriate.
 
 |
| Secondary Endpoints              |  |  |
| Duration of Response (or TTHR)   | 
 
FAS subjects who achieved CR/CRh* in first 2 cycles are included.
 
Cumulative incidence function considering competing risk will be provided when sample size is appropriate.
 
                 | 
 
Censoring at the time of HSCT may be considered as deem as appropriate.
 
  |
| Received AlloHSCT                | 
 
Summary statistics of proportion of AlloHSCT in FAS.
 
   |  |
| Best overall response (ORR)      | 
 
Summary statistics of ORR within first 2 cycles. FAS subjects without response will be included.
 
The rate will be estimated along with its 95% exact CI.
 
  | 
 
Additional sensitivity analysis will be conducted and will exclude those subjects without any post-baseline response assessment.
 
                               |
| Overall survival                 | 
 
FAS subjects will be used
 
K-M estimates will be used and 3, 6 and 12 months rates will be provided.
 
  | 
 
Censoring at the time of HSCT may be considered as deem as appropriate.
 
  |
| RFS                              | 
 
FAS subjects who achieved CR /CRh* in the first 2 cycles are included.
 
K-M estimates will be used and 3, 6 and 12 months rates will be provided when sample size is appropriate.
 
      | 
 
Censoring at the time of HSCT may be considered as deem as appropriate.
 
  |
| 100-day mortality after alloHSCT | 
 
Subset of subjects who undergo an alloHSCT in the FAS will be included. 1 minus the K-M survival estimate at day 100 will be provided when sample size is appropriate.
 
                                |  |
| Exploratory Endpoints            |  |  |
| MRD response                     | 
 
Summary statistics of MRD response in FAS. The rate will be estimated along with its 95% exact CI. Response rate is based on the number of subjects with a CR/CRh* and evaluable MRD.
 
          |  |
| Complete MRD response            | 
 
Summary statistics of Complete MRD response in FAS. The rate will be estimated along with its 95% exact CI. Response rate is based on the number of subjects with a CR/CRh* and evaluable MRD.
 
 |  |

**Table 5. Efficacy Endpoints Summary for Expansion cohort**

| Expansion Cohort Endpoint   | Primary Summary and Analysis Method   | Sensitivity Analysis   |
|---|---|--|
| Secondary Endpoints  |   |  |
| CR/CRh* for adult subjects or M1 remission for pediatric subjects | 
 
Summary statistics of CR/CRh* rate for adult subjects or M1 remission rate for pediatric subjects within the first 2 cycles.
 
Sub-categories will also be provided. The rate will be estimated along with its 95% exact CI. EAS subjects without response data will be treated as non-responders.
 
 | 
 
Repeat the analysis for subjects in the EAS who had non-missing post-baseline response data.
 
 
May repeat the analysis for PPS when deemed appropriate.
 |
| Exploratory Endpoints                                      |   |  |
| MRD response  | 
 
Summary statistics of MRD response in EAS analysis set. The rate will be estimated along with its 95% exact CI. Response rate is based on the number of subjects with a CR/CRh* and evaluable MRD.
 
  |  |

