**AMGEN** 

Date: 20 March 2019 Page 64 of 122

Table 6. Schedule of Assessments: Phase 1b/2

Examination a	Screening / Pre-phase	Treatment Period: Each Cycle (Day 1-42)	SFU Visit	Long-Term FU Efficacy/ Survival n			
		End of Infusion	Treatment- Free Interval	30 Days After Last Dose	3, 6, 9, 12, 18, 24 Months After completion of SFU visit		
Protocol-required therapy		Continuous 4 week infusion	Continuous 4 week infusion				
Subject writing sample (adult subjects only) k		Continuously throughout the study					
Adverse event/serious adverse event assessment	Х	Continuously throughout the study	Х				
Concomitant medication m	Х	Continuously throughout the study	Х	Х			
Disease/survival status		Continuously throughout the study			Х		

Page 2 of 2

aPTT = activated partial thromboplastin time; CNS = central nervous system; ECOG = Eastern Cooperative Oncology Group; HAMA = human anti-mouse antibodies; INR = international normalized ratio; MRD = minimal residual disease; SFU = safety follow-up.

<sup>a Assessments should be performed on specified day of each treatment cycle unless otherwise stated via a footnote.

<sup>b Vital signs (ie, systolic/diastolic blood pressure, pulse rate) and temperature collected every 12 hours during cycle 1, D1 and D2, once daily on D1 and D2 for each subsequent cycle. Vital signs collected at cycle 1, D8 only if dose step is performed and the SFU visit.

c Height and weight performed pre-dose on D1; however, this can be done the day before. Weight only performed at SFU visit. Height (in cm) and weight (in kg) should be measured without shoes

<sup>d Lumbar puncture/ intrathecal CNS prophylaxis within 1 week (+ 3 days) prior to start of blinatumomab therapy AND following each treatment cycle (after bone marrow aspirate on D29).

<sup>e Completed only if bone marrow aspirate was not performed as part of standard of care and a sample was provided for hematological and MRD assessment at the central lab. Bone marrow aspirate/biopsy will be performed at the SFU visit, if the subject ended treatment for any other reason than relapse. If a subject has not relapsed by day 29 (D29) of their last treatment cycle, bone marrow aspirate should be performed every 3 months until relapse. D29 bone marrow aspirate/biopsy for MRD on cycles 1 and 2 only. D29 bone marrow aspirate/biopsy for cytomorphology on every treatment cycle.

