#### 7.2.9 Bone Marrow Biopsy/Aspiration

Bone marrow will be used for hematological assessment and for evaluation of MRD by PCR. The following samples will be obtained for cytomorphological assessment and MRD measurement:

- Cytomorphology: BM smears (slides) at screening and at the end of each treatment cycle. In case of insufficient quality of the aspiration material at the end of each treatment cycle, a core biopsy should be performed before treatment start in the next cycle or at the safety follow-up visit, if the subject has not progressed and no further treatment cycles are to be administered.
- MRD: aliquots for PCR (individual rearrangements), at screening (if not performed as part of routine testing) and at the end of the first and second treatment cycles will be collected and analyzed at a central lab.

If a marrow aspiration is not possible, or the aspirate does not contain any BM, a core biopsy will be done. In case of core biopsies, no central MRD assessment will be possible due to the need to preserve the biopsy with formalin before shipment.

If a subject has not relapsed by their last induction and consolidation treatment cycle, a BM biopsy or aspirate should be performed every long-term follow-up visit until relapse.

The degree of bone marrow infiltration defined by the percentage of leukemic blasts in bone marrow will be evaluated by local laboratories as per cytological assessment. In addition, the bone marrow slides will be provided to the designated central laboratories for hematological assessment. The B-precursor phenotype has to be confirmed by the central laboratory by immunocytochemistry. The following markers will be analyzed as needed: CD3, CD5, CD10, CD13, CD19, CD23, CD33, CD34, CD79A, POX, TDT.

The results of the local laboratory are applicable for inclusion into the study and for the decision if pre-treatment should be administered if the results of the central laboratory are not yet available at the time these decisions are made.

Known cytogenetic and molecular aberrations will be documented in the case report form (CRF).

Results of additional tests routinely conducted by the investigators, but not required by the protocol such as immunophenotypic, cytogenetic or molecular analyses conducted during the study, will be collected and documented in the CRF.

All BM assessments will be performed at time points outlined in the Schedule of Assessments (Table 6).

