## 10.4.5 Exploratory Endpoints

MRD response and MRD complete response will be summarized based on FAS. The rate will be estimated along with its 95% exact CI. Additional sensitivity analysis will be conducted and will exclude those subjects without any post-baseline response assessment.

Product: Blinatumomab

Date: 20 March 2019 Page 97 of 122

Peripheral blood lymphocyte subsets and neurological exam abnormalities and findings will be summarized based on FAS.

MRD response is also an exploratory endpoint for the expansion part of the study and will be analyzed as described above, based on the expansion analysis set.

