### **Blast free hypoplastic or aplastic bone marrow**

For adult subjects:

Less than or equal to 5% blasts in the bone marrow, No evidence of disease, and insufficient recovery of peripheral blood counts: platelets  $\leq 50,000/\mu\text{L}$  and/or ANC  $\leq 500/\mu\text{L}$ .

For pediatric subjects, this treatment outcome will be considered as part of M1 remission.

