### 10.6.3 Analyses of Exploratory Endpoints

MRD response and complete MRD response will be summarized based on **FAS for phase 1b/2**. For expansion cohort, analysis for MRD response will be based on **EAS. Response rate is based on CR/CRh\* responder who have evaluable MRD assessment**. The rate will be estimated along with its 95% exact CI.

Peripheral blood lymphocyte subsets and neurological exam abnormalities and findings will be summarized based on FAS.

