## 11. Changes From Protocol-specified Analyses

- The clarification of primary efficacy endpoint for adult subjects (both Phase 1b and Phase 2) to be CR/CRh\*. The terms of “complete remission”, “CR”, “CR/CRh\*/CRi”, “CR/CRh\*” were used interchangeably in the protocol.
- The clarification of primary efficacy endpoint for pediatric subjects to be M1 remission.
- The clarification of RFS and Duration of Response endpoints for subjects who met primary efficacy endpoint (CR/CRh\* for adult subjects and M1 remission for pediatric subjects).
- **Sensitivity analysis for MRD response and complete MRD response is not performed because main analysis has already excluded subjects without any post-baseline response assessment.**

---

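### The SAP labels the MRD rates as FAS/EAS analyses but computes them only among CR/CRh* responders with evaluable MRD, and the pediatric denominator is unclear

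*SAP*

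**What the plan says.** Protocol Section 10.4.5 states: "MRD response and MRD complete response will be summarized based on FAS". It adds a sensitivity analysis that leaves out subjects with no post-baseline response assessment. For the expansion part, MRD response "will be analyzed as described above, based on the expansion analysis set".

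SAP Tables 3 and 4 (MRD response and complete MRD response) and Table 5 (MRD response) place the analysis in the FAS or EAS. The same cells then say: "Response rate is based on the number of subjects with a CR/CRh* and evaluable MRD". SAP Section 10.6.3 repeats this in substance, limiting the rate to a CR/CRh\* "responder who have evaluable MRD assessment".

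SAP Section 11 drops the MRD sensitivity analysis on the ground that the "main analysis has already excluded subjects without any post-baseline response assessment".

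On sampling, footnote e to Protocol Table 6 reads "D29 bone marrow aspirate/biopsy for MRD on cycles 1 and 2 only". Protocol Section 7.2.9 says that MRD aliquots "at the end of the first and second treatment cycles will be collected and analyzed at a central lab".

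The pediatric response endpoint is M1 remission. Under blast-free hypoplastic or aplastic marrow, SAP Section 6 says: "For pediatric subjects, this treatment outcome will be considered as part of M1 remission".

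**The concern.** The FAS is every subject who received any infusion. A rate over responders with an evaluable MRD sample is a different quantity: it describes depth of remission among those who remit. Under a FAS or EAS label it can be read as the chance that a treated patient reaches MRD response.

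The reason given for dropping the sensitivity analysis does not hold. The protocol's version removes only unassessed subjects. The SAP denominator also removes assessed non-responders and responders without evaluable MRD. Section 11, where departures from the protocol are recorded, does not mention the responder restriction. Both MRD endpoints are still planned; what is missing is both denominators that the protocol gave them.

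Some MRD responders can also drop out of view. Neither sampling provision depends on response, and the MRD response definition in SAP Section 6 has no count-recovery condition. An adult with blast-free marrow, low counts and MRD below 10⁻⁴ meets that definition but is in neither the numerator nor the denominator of the SAP rate.

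For children, the MRD rows of Tables 3 and 5 name only CR/CRh\*, although the response rows of the same tables also name M1 remission. SAP Section 6 requires count recovery for CR and CRh\*. The protocol's pediatric CR (Section 7.2.10.2 and Appendix F) includes M1 marrow without it. Two programmers could choose different denominators. Table 4 is adults only, so this part does not apply there.

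**Working it through.** **Interval method.** The plan uses exact (Clopper-Pearson) 95% limits: the 0.025 quantile of Beta(x, n−x+1) and the 0.975 quantile of Beta(x+1, n−x). All five rows of SAP Table 1 reproduce, for example 6/21 = 28.6% (11.3–52.2) and 14/21 = 66.7% (43.0–85.4). The documents state no MRD rate or power for this trial, so there is no planned MRD figure to reproduce.

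**The three rates.** Let N = treated, U = treated with no post-baseline assessment, R = CR/CRh\* responders, E = responders with evaluable MRD, m = MRD responders among E, and h = MRD responders outside CR/CRh\*. If no responder lacking evaluable MRD counts as an MRD responder:

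- Protocol main analysis: (m + h)/N
- Protocol sensitivity analysis: (m + h)/(N − U)
- SAP: m/E

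If E = R and h = 0, the SAP rate divided by the FAS rate is N/R.

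**Phase 2.** N = 21 and R are taken from SAP Table 1. The MRD counts are assumptions, shown as a range.

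| R of 21 | Ratio 21/R | All responders MRD-negative: SAP vs FAS | Half MRD-negative: SAP vs FAS |
|---|---|---|---|
| 6 | 3.5 | 100% vs 28.6% (11.3–52.2) | 50% vs 14.3% (3.0–36.3) |
| 8 | 2.6 | 100% vs 38.1% (18.1–61.6) | 50% vs 19.0% (5.4–41.9) |
| 12 | 1.75 | 100% vs 57.1% (34.0–78.2) | 50% vs 28.6% (11.3–52.2) |
| 14 | 1.5 | 100% vs 66.7% (43.0–85.4) | 50% vs 33.3% (14.6–57.0) |

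**Is the dropped sensitivity analysis redundant?** Assume 21 treated, 2 unassessed, 8 CR/CRh\*, 6 of those MRD-evaluable, 5 with MRD response, and none outside CR/CRh\*.

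- FAS: 5/21 = 23.8% (8.2–47.2)
- Protocol sensitivity: 5/(21 − 2) = 5/19 = 26.3% (9.1–51.2)
- SAP: 5/6 = 83.3% (35.9–99.6)

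The sensitivity rate stays close to the FAS rate and far from the SAP rate.

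**Earlier pediatric study (Protocol Section 2.1.2).** Inputs: 39 treated, 12 CR, 5 complete MRD responses among the CR subjects, and 2 further subjects with blast-free marrow. The reported figures reproduce: 12/39 = 30.8% (17.0–47.6) against 31% (17–48), and 5/12 = 41.7% against 42%.

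- Among CR subjects: 5/12 = 41.7% (15.2–72.3)
- Among all treated: at least 5/39 = 12.8%, or (5 + 2)/39 = 17.9% if both blast-free subjects were also MRD-negative. MRD status outside CR is not reported.

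**Pediatric denominator on the same data.** Assume the 2 blast-free subjects would be classed as M1 remission and are MRD-evaluable.

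- Count recovery required: 5/12 = 42%
- M1 remission: between 5/14 = 36% and 7/14 = 50%

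**The case against.** The SAP states its denominator openly, in the same cell as the FAS/EAS label, and both documents elsewhere start from the FAS and then narrow it. RFS and TTHR are limited to FAS subjects who responded, and 100-day mortality to those transplanted. In those places the narrowing is written into the protocol. Section 10.4.5 has no such words, and its sensitivity analysis makes sense only if the main analysis includes unassessed subjects. The restriction is therefore visible, but it is an undeclared departure.

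The full-set figure might still be recovered. Individual data will be listed, and the FAS summary may show counts. That is possible, but a listing is not a planned rate with an interval.

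Sampling is not wholly independent of outcome: Protocol Section 6.6 waives the marrow on premature discontinuation with documented progressive disease. This exception is narrow.

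Few MRD responders are likely to lie outside CR/CRh\*. Blast-free marrow without recovery was 2/39 (5%) in the earlier pediatric study and 3 subjects (8%) in the earlier adult one. That limits the loss from the numerator; the change of denominator is untouched.

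The pediatric example depends on how the two blast-free subjects would be classed. Both documents also have a hypocellular or acellular category for children that is defined as not M1. The figures are therefore illustrative, but the wording still has two readings.

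Last, a responder-conditional rate is useful and matches how the earlier pediatric study was reported. That stands, and the rate should be kept.

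**Conclusion.** The concern holds. As written, the SAP reports under a FAS or EAS label a rate that is not over the FAS or EAS. It plans neither of the protocol's two denominators, and its reason for dropping the sensitivity analysis is incomplete. At the SAP's own Table 1 counts of 6 to 14, the inflation relative to the FAS rate is 3.5-fold down to 1.5-fold. This assumes that every responder has evaluable MRD and that no MRD response occurs outside CR/CRh\*. The pediatric denominator in Tables 3 and 5 and Section 10.6.3 is not fixed by the text. The endpoints are exploratory, so the Phase 2 test and sample size are unaffected. This should be corrected, but it does not threaten the trial's main conclusion.

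**What to change.** In SAP Tables 3 to 5 and Section 10.6.3:

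1. Report the MRD response rate, and in Tables 3 and 4 the complete MRD response rate, over all FAS or EAS subjects whatever their hematological response. Count missing MRD as non-response. This rule is a proposal that mirrors the primary-endpoint rule (Protocol Section 10.4.2, SAP Section 9.3); the protocol does not state it for MRD. Because a core biopsy allows no central MRD assessment (Protocol Section 7.2.9), show the number without evaluable MRD beside the rate, so that technical failure is not mistaken for treatment failure.
2. Keep the conditional rate as a separate row, with its denominator named as CR/CRh\* (adults) or M1 remission (children) with evaluable MRD.
3. Restore the protocol's sensitivity analysis, or list in Section 11 both the restriction to responders and the removal of that analysis.

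The cost is a few lines of SAP text, one extra table row per endpoint and one line in Section 11 if the analysis is not restored. No new data are needed. The full-set percentage will be lower than the conditional one.

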**10.6.1 Analyses of Primary Efficacy Endpoint**

The primary efficacy endpoint in the study is CR/CRh\* for adult subjects or M1 remission for pediatric subjects within the first 2 cycles of blinatumomab treatment. The analysis is based on the response evaluation recorded in the eCRF for subjects in the FAS. The best response within the first 2 cycles will determine the primary efficacy endpoint. The subjects without evaluable response assessment will be included and treated as missing response status. The rate will be estimated along with its 95% exact CI. Summary of other best responses status by each response category will also be provided.

Sensitivity analyses may be performed by repeating the above analyses for subjects who had non-missing post-baseline response assessments and for PPS.

**10.6.2 Analyses of Secondary Efficacy Endpoint(s)**

When sample size is deemed appropriate (ie, at least 10 subjects), RFS and OS will be summarized by K-M method. Duration of response (or TTHR) will be estimated by the

nonparametric methods for estimating cumulative incidence function by treating the death not due to PD as a competing risk (Hosmer, Lemeshow, and May, 2008). OS will be performed on FAS and the event time will be calculated relative to the start date of blinatumomab infusion in the first treatment cycle. RFS and Duration of Response (or TTHR) will include subjects in the FAS who achieved CR/CRh\* (for adult subjects) or M1 remission (for pediatric subjects). The event time will be calculated relative to the date of bone marrow aspiration when response was detected for the first time in this study. For RFS and OS, three, six and twelve month survival rates will be provided. Additional summary considering the censoring at the time of HSCT may be considered for the sensitivity analysis purpose.

Proportion of subjects who undergo alloHSCT in remission due to treatment with blinatumomab will be summarized based on FAS. Subjects who receive an HSCT later during the long-term follow-up time of the study will be reported separately.

**When sample size is deemed appropriate**, the analysis of 100-day mortality after alloHSCT will be based on FAS with alloHSCT while in any CR following treatment with blinatumomab. The 100-day mortality rate after alloHSCT will be estimated by taking 1 minus the K-M survival proportion at day 100 on the subset of subjects who undergo an alloHSCT in the FAS.

**Secondary efficacy endpoints for expansion cohort in the study is CR/CRh\* for adult subjects or M1 remission for pediatric subjects within the first 2 cycles of blinatumomab treatment. Analysis of these endpoints based on Expansion analysis set (EAS) will be the same as for primary efficacy endpoints in phase 2.**

### 10.6.3 Analyses of Exploratory Endpoints

MRD response and complete MRD response will be summarized based on **FAS for phase 1b/2**. For expansion cohort, analysis for MRD response will be based on **EAS. Response rate is based on CR/CRh\* responder who have evaluable MRD assessment**. The rate will be estimated along with its 95% exact CI.

Peripheral blood lymphocyte subsets and neurological exam abnormalities and findings will be summarized based on FAS.

### 10.7 Safety Analyses

Safety analyses will include blinatumomab administration, adverse events, concomitant medications, laboratory measurement, vital signs, and antibody testing. Statistical analyses of safety will be carried out on the safety analysis set. No statistical

comparison of the overall incidence of adverse events will be done between dose cohorts.

Results of physical and neurological examinations and the writing test will be listed only. All data of HAMA assessments, hospitalization, anti-blinatumomab immunogenicity testing and pregnancy tests will be listed only.

The regular assessments of CSF and the CNS event related CSF assessments will be listed only.

**Safety assessments (as defined above), for Phase 1b (adults and pediatrics), Phase 2 (adults) and Expansion cohort (adults and pediatrics) will be reported as illustrated in the sections below.**

